In response to the PHA recommendation, ATSDR began the multi-step process of determining the appropriateness of conducting an epidemiological study of specific childhood cancers and birth defects at Camp Lejeune. The first step was to determine which childhood health problems to study. Based on the scientific literature, ATSDR decided to focus on specific childhood cancers and birth defects: childhood leukemia, spina bifida, anencephaly, cleft lip and cleft palate.

The second step was to identify the children eligible for the study by doing a telephone survey. ATSDR decided on children born to women who were pregnant with them while living on the base during 1968–1985. The year 1968 is the starting point because that year North Carolina began computerizing its birth records. These records were used to identify children for the study. The end point is 1985 because the tainted wells were shut down that year.

The survey began in September 1999 and ended in January 2002. ATSDR surveyed by telephone the parents of 12,598 eligible children. This number was about 80% of the estimated total. Parents were asked if the child had had a birth defect or had developed a childhood cancer. A total of 99 cases of childhood leukemia, spina bifida, anencephaly, cleft lip and cleft palate were reported (Appendix II).

The third step was to confirm the children's health problem(s). ATSDR asked the parents who reported that their children had health problems of interest (or the children if they were now over 18) for access to their child's health records. These records are now under review. ATSDR has received records for 60 of the 99 children so far and has confirmed about 80% as being correctly reported.

The final step will be to conduct a case-control study. This study will include all confirmed cases of the birth defects and childhood cancers which are the focus of the study. The study will also include modeling of the water system to see which mothers did and did not receive the water with VOCs. Currently we do not know which mothers received the water with VOCs.

In summary, ATSDR has finished the survey and is now confirming the cases. These steps were needed to prepare for the larger study. There is enough information to proceed with the full study. Only the case-control study can establish whether VOC-tainted drinking water may cause the childhood health problems being studied.

Intended/Potential Use of Study Findings

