To date, information regarding the health effects of exposures to drinking water contaminated with TCE and PCE are extremely limited. The findings of this study at Camp Lejeune should further our understanding of the health effects of TCE or PCE exposure from community drinking water and will help us better focus our prevention efforts.

Study Design/Locations

ATSDR will conduct a case-control study of cases of childhood cancer or specific birth defects and a random sample of controls to assess the relationship between VOC exposure and the incidence of childhood cancer and birth defects in children born to parents while residing at Camp Lejeune from 1968 to 1985. Both cases and controls may currently reside anywhere in the United States.

Objectives

The overall objective of this study is to examine the associations between maternal exposures within a 1-year period before child's birth to TCE and PCE in drinking water at Camp Lejeune during the period of 1968-1985 and risk of specific birth defects and childhood leukemia (ALL) in offspring.

Hypotheses

1. a. There is no association between ever drinking TCE/PCE contaminated water during the first trimester and the risk of specific birth defects.

- b. There is no association between ever drinking TCE/PCE contaminated water during each trimester and the risk of leukemia (ALL).
- 2. a. There is no association between exposures to different concentrations of TCE/PCE in drinking water during the first trimester and the risk of developing specific birth defects.
 - b. There is no association between exposures to different concentrations of TCE/PCE in drinking water during each trimester and the risk of leukemia (ALL).
- 3. a. There is no association between exposures during the first trimester to ever/never or to different concentrations of TCE/PCE in drinking water, taking into account the amount of water used (i.e., showering, hand washing dishes) or consumed by the mother, and the risk of specific birth defects.
 - b. There is no association between exposures during each trimester to ever/never or to different concentrations of TCE/PCE in drinking water, taking into account the amount of water used (i.e., showering, hand washing dishes) or consumed by the mother, and the risk of leukemia (ALL).

METHODS

Study Rationale

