A 1999-2002 ATSDR survey located 12,598 children born to parents who resided at Camp Lejeune at any time during pregnancy between 1968 and 1985. Children eligible for the survey were those born at 28 weeks or more gestation to mothers who were pregnant while they lived in base housing at Camp Lejeune during 1968-1985. Survey respondents were asked basic demographic questions as well as if the child was diagnosed with cancer before age 20 or if the child was diagnosed with a birth defect before age 5. If the child had cancer or a birth defect, the type of cancer or birth defect was also collected. Parental reports of cancer and birth defects are being verified by reviewing medical records. If medical records are not available to confirm a case, we will use other appropriate documentation such as the birth certificate, death certificate, or information obtained from a recent doctor's visit (e.g., a dental visit for potential cleft cases or physical therapy records for potential spina bifida cases) (Appendices VI, VII, VIII). The following cases of selected birth defects and cancers have been reported: 35 neural tube defects (NTDs), 42 oral cleft defects, and 22 childhood leukemias. To date, records have been obtained for 20 NTDs (15 confirmed as having NTDs; 5 confirmed as not having NTDs), 1 was ineligible, 1 refused, and 13 are still pending. Records have been obtained for 23 oral cleft defects (20 confirmed as having oral cleft defects; 3 confirmed as not having oral cleft defects), 3 refused, and 16 are still pending. Records have been obtained for 17 childhood leukemias (12 confirmed as having leukemia; 5 confirmed as not having leukemia), 2 were ineligible, and 3 are still pending.

Eligibility (Participant inclusion/exclusion criteria)

Potential cases consist of children with the following birth defects or childhood cancers who were born to mothers who resided at Camp Lejeune during their pregnancies between 1968 and 1985: NTDs (consisting of anencephaly and spina bifida), oral clefts (consisting of cleft lip with and without cleft palate and cleft palate), and childhood leukemias. Familial cases of leukemia, children who were 20 years of age or older when diagnosed with leukemia, or children who were 5 years of age or older when diagnosed with NTDs or oral clefts will be excluded. Only confirmed cases will be included in the primary analyses. We will consider doing a secondary analysis including unconfirmed cases.

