Potential controls consist of children without these birth defects or childhood leukemias who were born to mothers who resided at Camp Lejeune during their pregnancies in the same time period and participated in the survey. We will attempt to enroll ten times as many controls as cases. One control group will be utilized for all of the cases of both birth defects and childhood leukemias. Control selection will be performed by using a randomization procedure. The only risk factor that has a skewed distribution is maternal age. At ages 30-34 and >34, the percentages of mothers who delivered at Camp Lejeune were approximately 7.5% and 2%, respectively (ATSDR 1998). Although maternal age has a skewed distribution in the study population, we could not match on this risk factor because we lacked information on maternal age for about 20% of the study population.

The order of preference for participants in the study is 1) the biological mother of the case or control child, 2) the biological father of the case or control child, or 3) the case or control child. If the biologic father is not the initial study respondent, we will also attempt to contact him to obtain more detailed information about his medical history, lifestyle habits, and occupational history.

Sample Size, Power, and Precision of Risk Estimates

For a sample size calculation, the values of the alpha error, beta error, and minimum meaningful effect size are selected, and the required sample size is calculated. However, since the number of exposed subjects and the total number of cases for each outcome cannot be increased, and the alpha and beta errors should be set as low as possible, the only parameter that can vary is the meaningful effect size. If the a.) alpha error

is set at 0.10 (i.e., 90% confidence interval) b.) beta error is set at 0.20 (i.e., 80% power) and c.) the expected exposure prevalence is 40%, the following ORs can be detected given the number of cases for each outcome:

- an OR of 4.3 or greater can be detected for 15 cases with NTDs and 450 controls and an OR of 2.85 or greater can be detected for 28 cases with NTDs and 448 controls,
- an OR of 3.5 or greater can be detected for 20 cases with oral cleft defects and 440 controls and an OR of 2.5 or greater can be detected for 36 cases with oral cleft defects and 432 controls, and

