- an OR of 5.15 or greater can be detected for 12 cases with leukemia and 444 controls and an OR of 4.3 or greater can be detected for 15 cases with leukemia and 450 controls.

An exposure prevalence of 40% is from the previous study of SGA at Camp Lejeune (ATSDR 1998; Sonnenfeld et al. 2001). It represents the percent of births born at Camp Lejeune that were estimated to ever have been exposed to PCE during the study period. Although we will not know for sure until after the water modeling is completed, it is expected that about half of the births were exposed to PCE. It is also expected that the levels of exposure to PCE varied over the study period such that there will be a significant range of exposures to PCE. The situation for TCE is less clear, and probably a large majority of the births were not exposed to TCE. Again, the TCE levels will vary over the study period so there will be a range of exposures.

All 79 children with the following confirmed or pending birth defects and childhood cancers who were born to parents residing at Camp Lejeune during their pregnancy between 1968 and 1985 will be recruited for the study: 28 NTDs, 36 oral cleft defects, and 15 leukemias. We expect a 90% participation rate because all of the participants took part in the Camp Lejeune Survey in 1999-2002 and gave permission to be contacted for future studies. Additionally, many survey participants have telephoned ATSDR to request the results of the survey and inquire about future studies. A 90% participation rate will yield 71 cases: 25 NTDs, 32 oral cleft defects, and 14 leukemias. Using one control group, we will attempt to enroll ten times as many controls as cases which will yield a comparison group of 710 children to allow

enough controls for the analyses.

Enrollment of Study Participants

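### The most favourable detectable odds ratios assume full participation and confirmation of every pending report; at the case counts the plan itself expects, their power is about 72–77%, not 80%

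*Protocol*

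**What the plan says.** All locations are in the Protocol.

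- **Sample Size, Power, and Precision of Risk Estimates.** With alpha 0.10 (a 90% confidence interval), 80% power and 40% exposure prevalence, six detectable ORs are listed, two per outcome. The NTD pair is 4.3 at 15 cases and 450 controls, and "an OR of 2.85 or greater can be detected for 28 cases with NTDs and 448 controls". Clefts have 3.5 at 20/440 and 2.5 at 36/432. Leukemia has 5.15 at 12/444, and "an OR of 4.3 or greater can be detected for 15 cases with leukemia and 450 controls".
- **Same section, later paragraph.** All 79 confirmed or pending children are to be recruited. Then: "A 90% participation rate will yield 71 cases: 25 NTDs, 32 oral cleft defects, and 14 leukemias". Ten controls per case gives 710 controls. No detectable OR is given for these counts.
- **Eligibility.** "Only confirmed cases will be included in the primary analyses". A secondary analysis with unconfirmed cases will be considered.
- **Study Population.** Records reviewed so far confirmed 15 of 20 NTDs, 20 of 23 clefts and 12 of 17 leukemias; 13, 16 and 3 reports are pending. The Justification for Study puts it that the agency "has confirmed about 80% as being correctly reported".
- **Objectives and Hypotheses.** The aim concerns "risk of specific birth defects and childhood leukemia (ALL) in offspring", and hypotheses 1b, 2b and 3b all name ALL. Eligibility and the power rows count childhood leukemias without restriction to ALL.

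**The concern.** The favourable row for each outcome (28, 36 and 15 cases) equals confirmed plus pending: 15 + 13, 20 + 16 and 12 + 3. It can be reached only if every child takes part and all 32 pending reports prove true. The plan expects neither. It assumes 90% participation a paragraph later, and its own record review rejected 13 of 60 reports. Because unconfirmed cases are kept out of the primary analysis, both losses apply to the analysis that these ORs are meant to describe.

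A reader of the power section cannot find the detectable OR for the sample the plan expects to analyse, and the smallest ORs shown are the ones most likely to be repeated. For leukemia there is a second gap: no count or detectable OR is given for ALL, the outcome the hypotheses name.

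**Working it through.** **Inputs.** Alpha 0.10 two-sided, power 0.80, control exposure p0 = 0.40, 90% participation, 710 controls, and the confirmation counts above.

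**Formula.** The power section does not name one. I used the two-proportion formula with the Fleiss continuity correction, where n is the number of cases and r is controls per case:

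- p1 = 0.4·OR / (0.6 + 0.4·OR); d = p1 − 0.4; c = (1 + 1/r)/d
- effective n′ = (n − c/2)²/n; p̄ = (p1 + 0.4r)/(1 + r)
- z = [d·√(n′r) − 1.645·√((r + 1)·p̄(1 − p̄))] / √(r·p1(1 − p1) + 0.24); power = Φ(z)

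**Reproducing the plan.** NTDs, 28/448, OR 2.85: r = 16, p1 = 1.14/1.74 = 0.655, d = 0.255, c = 4.16, n′ = 23.99, p̄ = 0.415, z = 0.844, power 80.1%.

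| Stated row | Stated OR | Power at stated OR | OR solved for 80% power |
|---|---|---|---|
| NTD 15/450 | 4.3 | 79.4% | 4.35 |
| NTD 28/448 | 2.85 | 80.1% | 2.85 |
| Cleft 20/440 | 3.5 | 80.1% | 3.50 |
| Cleft 36/432 | 2.5 | 79.5% | 2.52 |
| Leukemia 12/444 | 5.15 | 78.0% | 5.37 |
| Leukemia 15/450 | 4.3 | 79.4% | 4.35 |

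All six agree within 2 points. Without the correction the same rows give 84–87%, so the corrected formula is the one that fits.

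**Expected confirmed participants.** 0.9 × (confirmed + observed rate × pending):

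- NTD: 0.9 × (15 + 0.75 × 13) = 0.9 × 24.75 = 22.3
- Cleft: 0.9 × (20 + 20/23 × 16) = 0.9 × 33.91 = 30.5
- Leukemia: 0.9 × (12 + 12/17 × 3) = 0.9 × 14.12 = 12.7
- Total 65.5

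**Favourable ORs at the expected counts, 710 controls.**

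| Outcome (OR) | Plan's 90% yield: cases, power, detectable OR | Confirmed participants: cases, power, detectable OR |
|---|---|---|
| NTD (2.85) | 25, 76.5%, 3.0 | 22.3, 71.5%, 3.2 |
| Cleft (2.5) | 32, 76.2%, 2.6 | 30.5, 74.3%, 2.7 |
| Leukemia (4.3) | 14, 76.8%, 4.6 | 12.7, 72.1%, 5.0 |

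For NTDs at 22.3 cases: r = 31.9, c = 4.04, n′ = 18.42, z = 0.567, power 71.5%.

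**Less favourable ORs at the same confirmed counts.** NTD 4.3: 94%. Cleft 3.5: 94%. Leukemia 5.15: 81%.

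**ALL.** The document gives no ALL count for this cohort. Its Childhood Leukemia section gives a general figure of 90% of childhood leukemia. Assuming 90–100%, the count is 0.9 × 12.7 = 11.4 up to 12.7. Power at OR 4.3 is 67–72% and the detectable OR is 5.6 down to 5.0. At 11.4 cases, power at OR 5.15 is 76%.

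**The case against.** Several points on the other side stand.

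- **The arithmetic is right.** The ORs are stated conditionally on listed counts and reproduce there. The fault lies in which counts were chosen.
- **The two rows bracket the expected counts.** A reader might infer that the plan overstates what it can detect throughout. The document does not support that. Three of the six rows use confirmed cases only and credit no pending report. They also omit participation (13.5, 18 and 10.8 cases if nothing further is confirmed, with power near 75%, 76% and 73%), but that case requires every pending report to fail.
- **The control numbers do no harm.** Using 432–450 controls rather than 710 is slightly conservative, by about 1 point of power. The 710 are already credited above.
- **71 is not an error.** A reader might want it replaced by 65. It is 90% of the 79 children to be recruited, pending ones included, and it sets the control target.
- **ALL.** The power rows say leukemia and never claim that every case is ALL. The literature summary describes the scope as childhood leukemia with emphasis on ALL. The mismatch can be resolved in either direction, and its size rests on a general percentage.
- **Limited consequence.** Case numbers cannot be increased, the Discussion concedes low power and wide intervals, and Data Analysis says interpretation will not rest on significance alone. But a general caveat does not supply the detectable OR for the expected sample.

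**Conclusion.** The point holds for the three favourable ORs. They rest on full participation and complete confirmation, against the plan's own 90% participation and confirmed-only primary analysis. Power there is about 76–77% after participation alone and about 72–74% after confirmation as well. The matching detectable ORs rise from 2.85 to about 3.2 (NTDs), from 2.5 to about 2.7 (clefts) and from 4.3 to about 5.0 (leukemia). The shift is modest for clefts and NTDs and larger for leukemia.

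The less favourable rows are conservative for the expected NTD and cleft counts and about right for all leukemia. Only a restriction to ALL could take the expected count below the 12-case row.

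The figures assume 40% exposure, 90% participation, and pending reports confirmed at the rates seen so far, which come from only 17 to 23 reviewed records per outcome. If every pending report were confirmed, the detectable ORs would be 3.0, 2.6 and 4.6; if none were, about 4.7, 3.7 and 6.0. The conflict between the ALL hypotheses and the all-leukemia counts is real whatever the ALL share.

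**What to change.** 1. In the power section, restate the detectable ORs for the expected confirmed participants with 710 controls: about 3.2 for NTDs (22 cases), 2.7 for clefts (30) and 5.0 for leukemia (13). State the participation and confirmation assumptions and name the formula. If the existing rows stay, label them as bounds.
2. Keep 71 as the enrolment figure and the basis for 710 controls. Add that about 65 are expected to enter the confirmed-only primary analysis.
3. Reconcile the leukemia hypotheses with the case definition and counts, either by aligning the hypotheses with all childhood leukemia or by defining ALL as the tested outcome. Give the count and detectable OR for whichever outcome tests hypotheses 1b–3b. If ALL, use the actual ALL count from the records; until then, about 11.4–12.7 cases and an OR of about 5.6–5.0.

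The cost is protocol text only. Recruitment, control selection and the planned models are unchanged; the stated detectable ORs become less favourable than the best ones now shown.

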The informed consent for the 1999-2002 ATSDR survey (IRB No. 2544) included a clause that ATSDR or their representative may contact the participants to ask them to take part in future studies (Appendix III). Potential participants will be informed about the study by an initial contact letter describing the purpose and design of the study (Appendix IV). Two weeks after the letters are mailed out; contractors will call the potential participants and invite them to take part in the study by participating in a 45 minute long telephone interview. If the initial study participant is not the child's father, we will also attempt to contact the child's father so we can get more detailed information about the father's medical history, lifestyle habits, and occupational history.

Data Collection

Trained interviewers will administer a telephone questionnaire using a computer-assisted telephone interview (CATI) instrument. The questionnaire will be administered to the biological mother of the case or control child; questions that ask about the biological father's lifestyle habits and medical and occupational history during the time period of interest will also be administered to the biological father if available to obtain more detailed information. A verbal informed consent will be obtained before the first question is read (Appendix V). The questionnaire will collect information on demographic and personal characteristics such as mother's residential history for a one year period before and after the birth of the index child; maternal drinking water and other home water usage; mother's pregnancy history of the index child (fever, prenatal care, medications, etc.); parental history of birth defects or having a previous child with a birth defect; maternal smoking, alcohol use, and occupation; and father's lifestyle habits and occupational history (Appendix V). Select variables collected in the 1998 study and the subsequent 1999-2002 survey (i.e., maternal residential history, child's date of birth, and highest level of education) will be pre-loaded into the CATI instrument and verified with the respondent. The collected information will be used to assign exposure status and to assess potential confounding.

A training manual describing interviewing techniques, intent and instructions for each question, and

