All electronically entered information obtained from questionnaires will be reviewed for missing data and ambiguous responses. Individual interviewers will be contacted to complete missing data where possible or to call back participants to fill in the missing information. Internal consistency and validity programs will be used to identify and correct coding and data entry errors. Data entry will be verified for accuracy by using software data match features.

Reimbursement

No remuneration will be offered to participants. In addition, no invasive procedures will be performed which could potentially cause injury or the need for medical treatment.

Data Analysis

The exposure variables include exposure status, concentration level, and/or percent of water from a contaminated source during specific time periods of interest in the one-year period before the child's birth. TCE and PCE will be evaluated separately. The exposure metrics will be ever/never, a categorization of the contaminant levels, and a categorical exposure variable that incorporates water usage and consumption as well as contaminant levels. Categorical exposure variables will be used because of the uncertainties involved in estimating exposures. We will look at the distribution of contaminant levels to determine appropriate cutoff values for the categorical variables. Those exposed to TCE or PCE will be compared to those without exposure to either chemical in the drinking water. Extensive sensitivity analyses will be conducted on the water modeling.

Descriptive statistics will be presented for the potential risk factors. Verified cases of birth defects and childhood cancers will be compared with controls using unconditional logistic regression. It may be necessary to use exact or conditional logistic regression methods if the data are too sparse. We will consider doing a secondary analysis including unconfirmed cases because the true odds ratio lies between the results obtained by analyzing only confirmed cases and confirmed and unconfirmed cases because unconfirmed cases are not all negative (do not have the condition) or all positive (do have the condition).

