Communicating results of environmental epidemiology studies to the general public is often complicated and challenging. Scientific concepts may be difficult for the general public to understand and there may be trust issues between the community and the federal government. To overcome these challenges, study participants will be informed of how ATSDR measured associations and the criteria used to interpret the meanings of the associations. Specifically, that odds ratios and confidence intervals were calculated for the different outcomes (birth defects and childhood cancer). Odds ratios compare the proportion of cases exposed to the proportion of controls exposed. If the proportions are the same (i.e., 1), there is no association between the exposure and the disease. If the proportion is higher in the cases (i.e., greater than 1), there is an association between exposure and disease. Confidence intervals assess the variability and precision of the odds ratio. The width of the confidence interval reflects the amount of variability in the odds ratio. Wider confidence intervals are less precise; narrower confidence intervals are more specific but less certain that the true odds ratio is within the confidence interval. If the confidence interval includes 1, then it is possible that the measured association was due to chance. The criteria used to interpret the meanings of those associations include:

- the strength of the association (the magnitude of the odds ratio),
- the consistency of findings, both within the study and when compared to other epidemiologic studies,
- dose-response effect (as concentration of TCE/PCE and/or the amount of water consumed increases, so does the risk of having a birth defect or childhood cancer), and
- when the exposure occurred the pregnancy and the duration of the exposure.

DISCUSSION

This is the first study to examine the associations between specific birth defects and childhood leukemia and exposures to VOCs in drinking water at Camp Lejeune. The proposed study has limitations and steps will be taken to reduce bias when possible. Efforts have been made to achieve a complete

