ascertainment of all cases of NTDs, oral clefts, and ALL. Even though the survey achieved a high participation rate of almost 80% of the total pregnancies that occurred at Camp Lejeune during the study period, the rates of birth defects and childhood cancers among the remaining 20% who did not participate is unknown (ATSDR 2003). The process of confirming the diagnoses of the potential cases is still ongoing. ATSDR will make the utmost efforts to enroll all confirmed cases in this study. Selection bias due to a low participation rate is not a potential problem, but confirming as many potential cases as possible will be key to the success of this study.

Computer modeling of the drinking water system at Camp Lejeune during 1968-1985 will provide ATSDR with extensive exposure information that is as accurate as possible. Errors in the recall of maternal residential address on base during pregnancy will not be a problem because housing records will be used to determine maternal residential address. However, recall bias is possible during the collection of historical water consumption and use habits. Additionally, recall of potential confounders may not be accurate because the time period of interest is 28-35 years in the past. To aid in the recall, participants will be prompted with specific activities associated with water consumption and use and with potential confounders.

To prevent interviewer bias, interviewers will be trained to adhere to the exact wording of the questionnaire. Interviewers will also be monitored on a regular basis during the administration of interviews to assure consistency. Furthermore, interviewers will not be aware of the case-control status of a subject and will be blinded regarding exposures status. Participants are interviewed on first contact when willing to do so. Interviewers will attempt to contact participants at different times of the day and different days of the week to minimize loss through non-contact.

The current study is likely to be constrained by a small sample size which would limit both the statistical power of the study to detect associations between in utero exposure to VOCs in drinking water and birth defects and childhood cancers and the ability to make inferences to other populations of pregnant women exposed to VOCs in drinking water. A small sample size will also likely result in wide confidence intervals of the effect measure.

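### Hypothesis 3 sorts only the exposed births by recalled water use, so a case-control difference in reporting could pass for a gradient by amount of water used; bring water use into the unexposed group as well

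*Protocol*

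**What the plan says.** Hypotheses 3a and 3b repeat the ever/never and concentration comparisons, "taking into account the amount of water used (i.e., showering, hand washing dishes) or consumed by the mother". Data Analysis turns this into the third exposure metric, "a categorical exposure variable that incorporates water usage and consumption as well as contaminant levels", and states the comparison for exposed births: "Those exposed to TCE or PCE will be compared to those without exposure to either chemical in the drinking water". No split of that reference by water use is stated, and no adjustment for use.

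The use data come from the telephone interview, whose topics include "maternal drinking water and other home water usage" (Data Collection). The same questionnaire goes to cases and controls, so use is also recorded for births with uncontaminated water. Before the interview, participants receive "an initial contact letter describing the purpose and design of the study" (Enrollment of Study Participants).

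The Discussion says that "recall bias is possible during the collection of historical water consumption and use habits". When it turns to recall of confounders it adds that "the time period of interest is 28-35 years in the past", and the same interval applies to water use. Its remedies are prompting, interviewer training and blinding of interviewers. The sensitivity analyses named in Data Analysis concern the water model. Residence is taken from housing records.

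Data Analysis bases interpretation on the size of the odds ratio and the exposure-response relationship, not on significance testing alone. Dissemination of Results words the dose-response criterion as "as concentration of TCE/PCE and/or the amount of water consumed increases, so does the risk".

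**The concern.** Recalled use decides which exposed category a birth falls into but plays no part in the reference. Any difference between cases and controls in reported use moves exposed cases between the low-use and high-use categories and leaves the reference where it is. The difference could come from recall, since respondents know the child's outcome and have been told the purpose of the study, or from a real difference in habits. Either way it appears as a contrast between the exposed categories and can be read as an effect of the amount of contaminated water used.

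The protocol names exactly that gradient as a criterion for interpretation. Prompting may improve recall, and blinding restrains the interviewer, but neither removes a difference on the respondent's side. The births exposed to neither chemical could show whether reported use differs between cases and controls in the absence of contamination, but the stated comparison does not use their answers in this way.

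**Working it through.** **The plan's own figures.** The protocol gives no figure for Hypothesis 3 or for recall bias. Its only computed figures are the detectable ORs (two-sided alpha 0.10, 80% power, 40% exposed). The continuity-corrected two-proportion formula gives 4.35, 2.85, 3.50, 2.52, 5.37 and 4.35, against 4.3, 2.85, 3.5, 2.5, 5.15 and 4.3 stated. They reproduce closely and are not in question.

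**Inputs from the protocol.** Expected cases: 25 NTDs, 32 oral clefts, 14 leukemias, 71 in all. Controls: 710. Exposure prevalence: 40% in the power calculation, with about half expected for PCE.

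**Assumed inputs.** The water has no effect, and true use is unrelated to exposure. A share c of control respondents and a share q of case respondents report high use. The protocol gives neither; c = 50% is the main setting, with 30% and 67% as a range.

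**Expected odds ratios under no effect.** With the same exposure prevalence in cases and controls, against all unexposed births:

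- OR(low use) = (1 − q)/(1 − c)
- OR(high use) = q/c

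| c | q | OR low | OR high | high:low |
|---|---|---|---|---|
| 50% | 50% | 1.00 | 1.00 | 1.00 |
| 50% | 55% | 0.90 | 1.10 | 1.22 |
| 50% | 60% | 0.80 | 1.20 | 1.50 |
| 50% | 65% | 0.70 | 1.30 | 1.86 |
| 50% | 75% | 0.50 | 1.50 | 3.00 |
| 30% | 45% | 0.79 | 1.50 | 1.91 |
| 67% | 82% | 0.55 | 1.22 | 2.23 |

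For example, at q = 60%: 0.40/0.50 = 0.80 and 0.60/0.50 = 1.20. The ever/never OR is 1.00 in every row.

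**Sampling behaviour.** Simulated studies with 25 cases and 710 controls, no effect, c = 50%, 0.5 added to each cell:

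| q | high:low ≥ 1.5, 50% exposed | high:low ≥ 1.5, 40% exposed | steady rise (1 < low < high), 40% exposed |
|---|---|---|---|
| 50% | 23% | 25% | 16% |
| 60% | 49% | 49% | 19% |
| 65% | 63% | 61% | 18% |

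Reporting bias therefore makes a contrast between the exposed categories much more likely, but hardly changes the chance of a steady rise from the reference. A positive trend at the two-sided 10% level goes from about 5% of studies to 11-13% at q = 65% (14 to 32 cases).

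**With use in the model for all births.** Compare exposed with unexposed births at the same reported use. If case respondents over-report equally in exposed and unexposed areas, both ORs are 1.00 and the bias moves to the use term: q(1 − c)/[c(1 − q)] = 1.50 at q = 60% and 1.86 at q = 65%. If only exposed cases over-report, 0.70 and 1.30 remain at q = 65%, and the use OR among unexposed births is 1.

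**Precision of the negative control.** With half of births unexposed there are 35.5 cases and 355 controls, split evenly by use. SE(log OR) = √(4/35.5 + 4/355) = 0.35, and exp(1.645 × 0.352) = 1.78. The 90% CI is about a factor of 1.8 either way.

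**The case against.** The protocol does not write out that the reference pools all levels of use. That is the natural reading of a single reference group, but taking water use into account could also mean adjustment, and the construction of the index may be left to an analysis plan that is not shown. A reference with no contaminant is also coherent if the metric is meant as intake: clean water delivers none at any level of use. The protocol discloses the recall problem and blinds interviewers to case and exposure status.

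A reader might infer that biased recall alone will produce the dose-response pattern that the plan counts as evidence. The document does not support that. It says recall bias is possible, not that it occurs, and gives no size. Reporting error that is equal in cases and controls creates no gradient when there is no effect. The biased pattern, read from the reference, is 1.00, 0.80, 1.20: it dips before it rises. Hypotheses 1 and 2 do not use recalled water use, and Dissemination of Results lists consistency within the study as a criterion, so a gradient under Hypothesis 3 beside null results for the other two should raise doubt.

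These objections limit the claim but do not remove it. The stated comparison gives no way to tell a reporting difference from an effect of the contaminant within the exposed categories, and the interpretation criteria name amount consumed without that caution.

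**Conclusion.** The point holds in a limited form. As stated, the Hypothesis 3 comparison is open to a false contrast between low-use and high-use exposed births if cases and controls report use differently. With reporting shares of 60% and 50% the expected ORs are 0.80 and 1.20, a 1.5-fold contrast; with 65% and 50% they are 0.70 and 1.30. With 25 cases, the chance of seeing at least a 1.5-fold contrast rises from about 23% to 49% or 63% at 50% exposed, and is much the same at 40%.

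This rests on an assumed size of reporting difference, on use unrelated to exposure, and on a reference group pooled over use. It does not extend to Hypotheses 1 and 2, and it does not mean that a steady rise from the reference is to be expected. It matters because the protocol reads exposure-response, including amount of water consumed, as a main ground for interpretation, and because the data for a check will already have been collected.

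**What to change.** 1. In Data Analysis, keep the planned contrast for Hypothesis 3 and add a model in which reported water use enters as a main effect for all births, unexposed births included, so that exposed and unexposed births are compared at the same reported use.
2. Report the high-versus-low-use OR, with its 90% CI, among births exposed to neither chemical, pooled over the three outcomes, as a negative control.
3. In Data Analysis and Dissemination of Results, state that a gradient by amount of water used is read alongside this OR and the results for Hypotheses 1 and 2, and is not taken alone as exposure-response.

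Do not make it a rule that a gradient counts only if it exceeds the negative-control OR. Both estimates are too imprecise: in simulation with 25 cases and no effect, the gradient exceeds the pooled negative-control OR about half the time, whether or not recall is biased.

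The cost is wording and wider intervals, with no new data. The negative control is itself imprecise, at about a factor of 1.8 either way. The adjustment removes the bias only if over-reporting is similar in exposed and unexposed areas, so a negative-control OR near 1 does not exclude over-reporting confined to exposed areas. The report should say so.
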